7.1 Specification of Safety Parameters

Recruitment and Informed Consent: The investigators have taken several steps to protect participants against potential risks inherent to the proposed research. First, every effort will be made to protect the confidentiality of participant records. We will obtain a Certificate of Confidentiality from the Federal government, because we are asking participants about the use of illegal drugs. However, complete confidentiality can never be absolutely guaranteed because records may be examined by personnel from the UNM Human Research Protections Office and because accidents or other unforeseen circumstances sometimes occur despite the best protections put in place. Participants will be informed of this possibility prior to signing any consent forms for this study. All records will be kept strictly confidential and will not be inspected by any other agency except if required by law. Only research staff and staff of the UNM Human Research Protections Office will have access to PHI. Signed consent forms will be kept separately from any documents containing Personal Health Information (PHI) or participants' unique ID numbers. The database linking ID numbers to participants' identity will be kept separately from all PHI and ID numbers and only the PI and research staff on this study will have access to this link. Any hard copies of data (e.g., consent forms, audiotapes of sessions) will be kept in double locked rooms designated for the storage of PHI. Data will be destroyed 7 years after the last publication. The results of this research may be presented at meetings or in publications, however participants' identities will not be disclosed. All computers with ID-coded data will be encrypted and password protected.

Distress. Potential psychological risks, including discomfort associated with disclosure of information, feelings of compromised privacy and distress that may be caused by increased awareness of one's opiate misuse, will be addressed in the consent form. Participants will be encouraged to contact investigators and/or study staff if they have any concerns about their participation or if they experience any psychological distress. All study investigators are clinical psychologists with extensive experience in the treatment of chronic pain and substance abuse and/or substance misuse, abuse, or dependence. They will train and supervise research staff and the study therapists to utilize data provided at each assessment point as well as clinical judgment to monitor and evaluate the condition of participants. Therapists will always have a list of licensed psychologists to call in the event of an emergency. If a participant discloses suicidal or homicidal intentions or ongoing child or elder abuse, the therapist will notify the licensed psychologist on call who will evaluate the participant for risk and follow the NM state law regarding mandated reporting. Therapists will disclose these limits of confidentiality to participants at their first therapy session. If a participant arrives for treatment or assessment in an intoxicated state, the therapist or research assistant will reschedule their session and be advised not to drive and seek appropriate transportation back to their homes. All participants will be informed of the right to withdraw from the study at any time and still receive full compensation for their time.

7.2 Methods and Timing for Assessing, Recording, and Analyzing Safety Parameters

N/A

7.3 Adverse Events and Serious Adverse Events

As noted above, we deem the risk of adverse events to be negligible within this study. Adverse events can include a breach of study procedures (e.g., use of an expired consent form), distress requiring the services of a healthcare provider, or inadvertent breach of confidentiality.

There is no evidence that participation in this treatment trial will increase risk of a serious adverse event.

All adverse events will be recorded and reported within 5 days of occurrence, as required by our IRB of record (<https://spa.unm.edu/common/documents/irb-guidelines.pdf>).

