In military veterans, the issues of chronic pain and opioid-related problems seem even more pronounced. Chronic pain is common, distressing, and debilitating, particularly in those that have served since the first Gulf War, with prevalence estimates reaching as high as 68%³⁸⁻⁴². As in civilian healthcare settings, opioids are commonly - and increasingly - used in the treatment of chronic pain in veterans^{38,43}, with one recent large scale study indicating that two-thirds (978 of 1,478) of veterans with a chronic pain diagnosis were prescribed opioids as part of their treatment⁴⁴. Furthermore, in that same study, half of those prescribed opioids (478 of 978) were receiving in excess of 180 mg total daily morphine milligram equivalents, a level that represents a substantial increase in overdose risk in comparison with lower dosages⁴⁵. There is evidence of a vicious cycle of comorbidity amongst chronic pain, opioid abuse, and adverse events in veterans^{46,47}. For example, in one study of over 6,000 veterans, the mere presence of a chronic pain diagnosis almost doubled the risk of prescription drug abuse (OR: 1.9; 95% CI: 1.4-2.5)⁴⁸, while another large scale survey of over 15,000 veterans indicated a prescription for opioids for chronic pain was related with an increased risk of adverse clinical outcome (e.g., accidents resulting in wounds, opioid-related accidents, overdose, violence-related injuries) in a manner that was independent of mental health diagnoses or other prescribed medications⁴³. Clinicians in Veteran Affairs (VA) hospitals are well aware of these issues and have noted both frustration and uncertainty in treating chronic pain patients, as well as the lack of evidence-based approaches that simultaneously treat problems related to both chronic pain and opioid misuse^{49,50}.

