15. In the past 30 days, how often have you borrowed pain medication from someone else?					
16. In the past 30 days, how often have you used your pain medicine for symptoms other than for pain (e.g., to help you sleep, improve your mood, or relieve stress)?					
17. In the past 30 days, how often have you had to visit the Emergency Room?					

©2008 Inflexxion, Inc.

Pain Behavior – Calibrated Items

Please respond to each item by marking one box per row.

In the past 7 days....

		Had no Pain	Never	Rarely	Sometimes	Often	Always
PAINBE2	When I was in pain I became irritable.....	1	2	3	4	5	6
PAINBE3	When I was in pain I grimaced	1	2	3	4	5	6
PAINBE6	When I was in pain I would lie down.....	1	2	3	4	5	6
PAINBE8	When I was in pain I moved extremely slowly.....	1	2	3	4	5	6
PAINBE9	When I was in pain I became angry.....	1	2	3	4	5	6
PAINBE11	When I was in pain I clenched my teeth.....	1	2	3	4	5	6
PAINBE13	When I was in pain I tried to stay very still.....	1	2	3	4	5	6
PAINBE16	When I was in pain I appeared upset or sad.....	1	2	3	4	5	6
PAINBE17	When I was in pain I gasped.....	1	2	3	4	5	6

Pain Interference – Calibrated Items

Please respond to each item by marking one box per row.

In the past 7 days...

		Not at all	A little bit	Some-what	Quite a bit	Very much
PAININ1	How difficult was it for you to take in new information because of pain?	1	2	3	4	5
PAININ3	How much did pain interfere with your enjoyment of life?	1	2	3	4	5
PAININ5	How much did pain interfere with your ability to participate in leisure activities?.....	1	2	3	4	5
PAININ6	How much did pain interfere with your close personal relationships?.....	1	2	3	4	5
PAININ8	How much did pain interfere with your ability to concentrate?.....	1	2	3	4	5
PAININ9	How much did pain interfere with your day to day activities?.....	1	2	3	4	5
PAININ10	How much did pain interfere with your enjoyment of recreational activities?.....	1	2	3	4	5

©2008-2012 PROMIS Health Organization and PROMIS Cooperative Group

BC-MDI

The following is a list of symptoms that you may have experienced. Consider your experience with these symptoms over the past two weeks, including today. Please rate each symptom marked in the severity scale (0 – 5).

0 Not a problem	1 Very Mild Problem	2 Mild Problem	3 Moderate Problem	4 Severe Problem	5 Very Severe Problem

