Rate how effective you were this past week in making progress in the areas of your life that matter to you.

Not at all 0 1 2 3 4 5 6 7 8 9 10 Most Effective

Weekly Diary (pg 2)

9. Are you currently taking Buprenorphine, Naloxone, or Suboxone Yes No

10. Are you currently in treatment for substance abuse or dependence? Yes No

If you checked "Yes", for which drug(s): _____

11. Since your last session with us, have you had any other treatments for pain? Yes No

If you checked "Yes", please complete the rest of this form:

Treatments for pain since last session (check all that apply):

____ Operations (Surgery) (how many? _____)	____ Injections (how many? _____)
____ Alterations or changes in pain medications	____ Physical therapy
____ Seen a Chiropractor	____ Osteopathy
____ Stimulator/Pump Implant	____ TENS Unit
____ Psychotherapy or Counselling Sessions	____ Acupuncture
____ Hypnosis	____ Hydrotherapy (Pool)
____ Other _____	

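### No systematic safety inquiry is specified for the opioid harms the protocol names, and no rule turns questionnaire answers into adverse event records, so a low event count could not be interpreted

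*Combined protocol and SAP*

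**What the plan says.** Section 7.2 carries the title "Methods and Timing for Assessing, Recording, and Analyzing Safety Parameters" and its whole content is N/A. Section 7.3 gives examples rather than a definition: "Adverse events can include a breach of study procedures (e.g., use of an expired consent form), distress requiring the services of a healthcare provider", and an accidental breach of confidentiality. It calls the risk negligible and requires reporting within 5 days of occurrence.

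Section 2.1 cites a large survey linking opioid prescription for chronic pain in veterans with "accidents resulting in wounds, opioid-related accidents, overdose, violence-related injuries". Under section 4.1, every participant takes prescribed opioids daily and has current misuse, abuse or dependence.

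The routes by which events could reach the study team are these:
- Section 7.1: "Participants will be encouraged to contact investigators and/or study staff if they have any concerns about their participation or if they experience any psychological distress". Research staff and therapists are also to use assessment data and clinical judgment to monitor participants.
- Section 4.2: a self-report screen for suicidal ideation at baseline, post-treatment and follow-up.
- COMM (Appendix IV), at the same three points: among others, "In the past 30 days, how often have you had to visit the Emergency Room", with further items on taking more than prescribed, thoughts of self-harm, and emergency calls or unscheduled clinic visits.
- Weekly Diary page 2 (Appendix IV): addiction medication, treatment for substance use, and "Since your last session with us, have you had any other treatments for pain".

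The forms in Appendix VIII and the log in Appendix IX have fields for hospitalization, life-threatening events and death. Section 10.3.4 gives protocol deviations their own log. Section 10.3.5 sends adverse events to the DSMB monthly.

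**The concern.** An adverse event count means something only if the plan says how events are sought, over what period, and what qualifies. Here the section meant to say so is left as N/A, the examples in 7.3 include no physical or opioid-related harm, and the schedule in section 6.1 has no safety row. If nobody asks, few events will be recorded, and the DSMB and the designers of the larger trial would have no means of telling a low rate from poor ascertainment. Listing an expired consent form as an adverse event adds a second problem, because paperwork errors could enter the same count as harm to participants.

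**Working it through.** **1. Is each harm named in section 2.1 asked about?** I set those harms against the visible forms.
- Overdose: no item. The nearest is the COMM item on taking more than prescribed, a rating from never to very often with no date, cause or outcome.
- Accidents, wounds, violence-related injury: no item. The nearest is the COMM emergency-room item, again a frequency rating without cause.
- Hospital admission: no item. The diary asks about pain treatments such as surgery or injections.
- Suicidal ideation: asked, through the section 4.2 screen and COMM item 5.

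Weekly Diary numbering jumps from 6 to 9, so two items cannot be seen. They are probably the mindfulness-practice and homework items described in the protocol summary.

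**2. Does a positive answer become an adverse event record?** Section 4.2 links significant ideation to a clinic contact. Nothing in 4.2, 7.1 to 7.5 or 10.3.5 says that an answer on the COMM, the diary or the ideation screen is reviewed for the adverse event form.

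**3. How much time does COMM recall cover?** Inputs: visits at weeks 13 and 37 (section 6.1) and a 30-day recall (Appendix IV).
- Baseline to week 37: 37 × 7 = 259 days.
- Two post-baseline administrations: 2 × 30 = 60 days; 60/259 = 23%. Outside recall: 259 − 60 = 199 days.
- Week 13 to week 37: 24 × 7 = 168 days; 168 − 30 = 138 days outside recall; 138/168 = 82%.
- Counting baseline as week 1 gives 36 × 7 = 252 days and 60/252 = 24%, so the convention hardly matters.

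These gaps are the same in both arms. Weekly contact falls within the first 13 weeks, but the visible diary items ask about none of these harms. After week 13 the only planned contact before the follow-up visit is a scheduling call one week ahead, so an event nobody reports in that interval cannot meet the 5-day requirement.

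**4. Is weekly contact confined to the therapy arm?** No. The compensation budget in section 6.2.5.1 covers weekly assessments for 64 participants in Year 1 and 56 in Year 2: 64 + 56 = 120, the full sample. The yearly totals reproduce:
- Year 1: 64 × 60 + 64 × 60 + 40 × 50 = $9,680.
- Year 2: 56 × 60 + 56 × 60 + 80 × 50 + 88 × 50 + 88 × 50 = $19,520.
- Year 3: 32 × 50 + 32 × 50 = $3,200.

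Planned contact over the treatment period:
- Therapy: 12 sessions × 1.5 h = 18 h, in ACT+MBRP only.
- Weekly assessment: 12 × 20 min = 4 h, in both arms.
- Total: 22 h in ACT+MBRP against 4 h in standard care.

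**5. What could a count of zero rule out?** With 120 participants and complete ascertainment, the one-sided 95% upper bound is 1 − 0.05^(1/120) = 2.5%. If only a fraction c of affected participants is recorded, the bound on the true rate becomes 2.5%/c (2.466% before rounding). The documents give no capture fraction. Over an assumed range of c = 90%, 60% and 30%, the bound is 2.7%, 4.1% and 8.2%. With c unknown, the bound is unknown.

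**The case against.** The strongest reply is that the plan is less empty than section 7.2 suggests. The examples in 7.3 are introduced as illustrations, not a closed list. The Appendix VIII and IX forms would accept an overdose admission once known. Suicidal ideation is screened three times, and several COMM items bear on harm. Section 7.1 has research staff as well as therapists monitoring participants from assessment data. Deviations already have a log, and section 10.3.4 sends them to the adverse event form only where appropriate. The harms in section 2.1 are background associations with opioid prescribing, which the trial does not alter, and the IRB accepted the investigators' minimal-risk assessment.

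Most of this stands, and it limits the point. A reader might infer that harms are captured only if volunteered. The ideation screen and the COMM proxies contradict that. A reader might also infer that detection occurs mostly in the therapy arm. The documents do not show it: weekly assessments are budgeted for everyone, both arms share the week 13 and week 37 visits, and no capture rates are given from which an excess could be calculated. How standard-care participants complete weekly measures is unclear, since section 6.2.4 ties them to each week's visit and the Appendix VI payment log labels all twelve weeks as therapy sessions. Unclear is not absent.

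The reply does not supply a method. Forms record events already known; they do not find them. Staff cannot monitor overdose or injury reliably from assessments that do not ask about either.

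**Conclusion.** The point holds in limited form. No systematic inquiry is specified for overdose, accidents or injuries, and no rule carries existing positive answers into adverse event reporting. COMM proxies recall 23% of the 259 days to week 37 and leave 138 of the 168 post-treatment days (82%) uncovered, in both arms. A low adverse event count would therefore be uninterpretable. Unequal detection by arm is a risk arising from 22 against 4 hours of planned contact. Its direction and size are not established.

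This rests on three assumptions: the COMM is given at week 13 as the protocol summary states, standard-care participants complete the weekly measures as budgeted, and the two unseen diary items are not safety questions. The matter should be corrected, but it does not threaten the feasibility aims.

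**What to change.** 1. In section 7.2, replace N/A with one short checklist, worded and administered identically in both arms: overdose, emergency visit, hospital admission, accident or injury, self-harm, and distress needing care. Put it on Weekly Diary page 2 beside items 9 to 11 and in the week 13 and week 37 batteries, with recall to the previous contact. State how standard-care participants complete the weekly form.
2. State that positive checklist answers, and positive COMM or ideation-screen answers, are reviewed for entry on the adverse event form.
3. In section 7.3, define an adverse event as an untoward occurrence in a participant in either arm. Record procedure breaches only on the Protocol Deviation Log unless they harm a participant.

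The cost is protocol wording, a few minutes per assessment, and more events to log and report, most of them probably unrelated to the intervention. Recall at week 37 would span 24 weeks, so dates will be imprecise, but the interval would at least be asked about.

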7.4 Reporting Procedures

The PI of the study ([name]) will be responsible for reporting all adverse events to the IRB of record. The IRB uses the "Click" system (<http://hsc.unm.edu/som/research/hrrc/click.shtml>), which includes a reporting mechanism that is sent directly to the IRB. For any adverse events, a course of remediation will be proposed (e.g., in the event of a protocol violation, safeguards will be put in place to decrease the probability of repeated violation) to the IRB, although the IRB itself will approve/disapprove the remediation.

7.5 Follow-up for Adverse Events

All AE's will be reported to the IRB of record within five days. Follow-up remediation will occur within five days of the IRB's response or decision.

7.6 Safety Monitoring

We have established a Data Safety Monitoring Board (DSMB), consisting of three individuals. The first member is [name], who is a Distinguished Professor within the Department of Psychology at UNM and also director of the Center on Alcoholism, Substance Abuse, and Addictions (CASAA). She brings with her 40 years of experience conducting funded clinical trials with substance abusing populations. The second member is [name], a Regents' Professor within the Department of Psychology at UNM. [name] also has extensive experience working with complex clinical populations, chiefly schizophrenia and brain injury. He is also a member of the UNM Institutional Review Board (IRB) and has expertise in research ethics. The third and final member is [name], a Research Professor within the Department of Psychology and CASAA, as well as Chair of the UNM IRB. [name] brings with him significant expertise in trial design and research ethics. He also is a highly accomplished statistician. Please see biosketches for all three members of the DSMB in Appendix VII.

8. INTERVENTION DISCONTINUATION

- Participant choosing to discontinue.
- Because this is a feasibility trial, we will not discontinue intervention based on non-attendance.

No other discontinuation criteria are identified.

Commented [KV3]: Need to add discontinuation criteria from the consent

9. STATISTICAL CONSIDERATIONS

[figure not shown]
9.1 General Design Issues

Preliminary Analyses: Data will be analyzed for missing cases to detect any bias across research groups that might result from differential attrition and/or response omission. For example, participant characteristics to include gender, minority status, age, drinking history, pain duration and intensity, educational achievement, and previous treatment experiences will be compared for those participants retained in the study versus those lost to attrition. Furthermore, the data will be examined for both missing cases and outlier scores on measures. Variable distributions will be checked for normality and if necessary, transformations will be performed to normalize the distributions. We will compare demographics and primary study measures at baseline between randomized treatment groups, using Analyses of Variance (ANOVA) for continuous variables (or Kruskal-Wallis if parametric assumptions are violated) and using chi-square tests for categorical variables. Subsequent analyses will adjust for significant baseline differences among the randomized groups at $\alpha = 0.05$.

Analyses to Test Primary Aim Hypotheses: The primary analyses for Aim 1 will be descriptive, including calculating the percent of individuals enrolled in the study versus those eligible and the percent of individuals who remain in the study. We will pay particular attention to issues of retention, as the treatment program will occur over 12 weeks and this length may impact treatment completion (previous programs of ACT alone, which have lasted eight weeks, have had drop-outs of < 20%^{17,21}). Therefore, we will define multiple levels of treatment retention, including partial treatment completion (% of individuals who do not complete all sessions), treatment dropout (% of individuals who dropout of treatment but continue to do assessments), research dropouts (% of individuals who remain in treatment, but do not complete research assessments), and treatment + research dropouts (% of individuals who do not complete treatment for research assessments). We will further break down the enrollment and retention calculations by examining enrollment/retention differences by treatment group, gender, age race/ethnicity, and initial severity using cross-classification tables.

Analyses to Test Secondary Aim Hypotheses. The primary goal of Aim 2 is to identify potential mechanisms of change and intermediate endpoints for future randomized clinical trials comparing ACT+MBRP to standard care. We will accomplish this goal by examining initial level and changes in targeted mechanisms over time during the course of treatment, as well as the association between changes in targeted mechanisms during treatment and 6-month follow-up measures of clinical outcomes. Targeted mechanisms will include (1) pain acceptance (2) psychological flexibility, (3) experiential avoidance, (4) opioid craving, and (5) reactivity to pain and craving, and will be examined using latent growth curve models with fixed effects of treatment and random effects of time. These analyses will provide an estimate of the initial level of each targeted mechanism (i.e., intercept) and the change in the targeted mechanisms over time (slope). Clinical outcome measures will include pain interference, pain behavior, and opioid misuse and will be examined using mediation analyses within the context of latent growth curve modeling⁶⁴, as we have done in prior studies^{63,65}. Specifically, as shown in simplified form in Figure 2, we will examine whether initial level (intercept) or changes (slope) in the targeted mechanisms ("M" in figure 2) during treatment mediate the effect of treatment on 6-month clinical outcomes, controlling for baseline levels of the outcomes. These analyses will also provide a test of Aim 2 Hypothesis 2, which is to identify those measures that are most sensitive to change (measures with the largest slope). Identifying measures that are more sensitive to change will help us in identifying intermediate endpoints for a larger RCT. Validation of intermediate endpoints is challenging and it is often recommended that meta-analytic methods be used⁶⁶, but alternative methods have been developed that allow for the evaluation of endpoints in mental-health clinical trials⁶⁷.

Figure 2. Simplified mediation model (excludes residual terms and covariances)

models will be estimated using the product of coefficients method⁶⁸, which provides an estimate of the mediated effect by multiplying regression coefficients for the regression of the mediators (e.g., slope of targeted mechanism) on treatment condition (i.e., a-path or α) and for the regression of the clinical

outcome on the mediators (i.e., b-path or β). We will use bootstrapping to obtain 95% confidence intervals of the mediated effect⁶⁹. We will use maximum likelihood estimation for all analyses, which provides the variance-covariance matrix for all available data and is the preferred method for estimation when some data are missing⁷⁰. Attrition analyses will determine whether there are any differences in study variables between those with missing and complete data. Study variables associated with missing data will be covaried in all analyses.

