9.6 Data Entry and Analyses

Data will be entered into the Statistical Package for Social Sciences Software (SPSS; IBM Corp). We will update the software license yearly so that the most recent version is used (currently version 22 is used). We will use an audit trail for entry, which will include a "sign-in" mechanism, where each session of data entry will be recorded. Recorded information within this mechanism will include the RA doing data entry, as well as case numbers entered and descriptive information with regard to the data entered (e.g., "cases 14-19; post-treatment data entered". A new database will be saved and individually labeled after each session of data entry (e.g., NCCIH R34 – Jan.22.2015).

In addition to responses to section 9.1 and 9.2, where details regarding the data analyses can be found, the following information addresses the queries listed in the instructional set for completing this protocol. We do not anticipate any confounding variables, although we will assess for the role of gender, age, ethnicity, educational achievement, pain duration, and pain location in influencing dependent variables.

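### Covariates for later analyses are picked by significance-testing the randomised arms at baseline; apart from the outcome's own baseline in the 6-month models, no prognostic covariate is fixed in advance

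*Combined protocol and SAP*

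**What the plan says.** Section 9.1, Preliminary Analyses, sets out the screening step: "We will compare demographics and primary study measures at baseline between randomized treatment groups". It uses ANOVA or Kruskal-Wallis for continuous variables and chi-square for categorical ones. The consequence follows: "Subsequent analyses will adjust for significant baseline differences among the randomized groups", with 0.05 as the threshold. The variables to be tested are not listed and no multiplicity control is stated.

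Four other statements bear on which covariates enter a model:

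- **Section 9.1, secondary-aim analyses.** The mediation models ask whether the mechanisms "mediate the effect of treatment on 6-month clinical outcomes, controlling for baseline levels of the outcomes". No significance condition is attached. The mechanism growth curves estimate initial level as the intercept and change as the slope.
- **Section 9.1, last sentence.** "Study variables associated with missing data will be covaried in all analyses". This is a second data-driven rule.
- **Section 9.6.** "we will assess for the role of gender, age, ethnicity, educational achievement, pain duration, and pain location in influencing dependent variables". No model is given.
- **Section 9.2.** The power calculation takes baseline as one of three repeated assessments in a mixed model.

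Allocation is by random blocks of 2, 4 and 6 (sections 6.2.2 and 9.2). For the primary aim, "The primary analyses for Aim 1 will be descriptive".

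**The concern.** Because the arms are formed by randomisation, every baseline difference between them is a chance event. A p-value below 0.05 measures how unlucky the draw was for that variable. It does not show whether the variable predicts the outcome, which is the reason to adjust for it. A strongly prognostic variable would be left out in about 95% of trials, and an irrelevant one would be let in about 5% of the time.

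Two things are at stake. The first is precision in the Aim 2 models, for covariates other than those the plan already fixes. The second is pre-specification: with the balance rule, the missing-data rule and the section 9.6 variables whose role is to be assessed, the Aim 2 models cannot be written down before the data are seen.

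The rule also suits mediation poorly. The path from treatment to mechanism is protected by randomisation. The path from mechanism to outcome is not, and needs covariates that predict both. Balance between arms says nothing about that.

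**Working it through.** **Inputs.** From section 9.2: 60 per arm, two-sided alpha 0.05, d = 0.25, three assessments, correlation among repeated measures 0.43. From section 9.1: pre-test alpha 0.05. Assumptions: the number of tested variables (5 to 20) and their independence; 0.43 as the baseline-to-follow-up correlation; d = 0.5 as a second illustrative effect; a partial correlation of 0.1 to 0.3 for a further covariate.

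**1. The plan's own figure.** A treatment-by-time F test with f = d/2 = 0.125 has noncentrality f² × N × m/(1 − ρ) = 0.015625 × 120 × 3/0.57 = 9.87 on 2 and 2 × 118 = 236 df. Power is 0.805, so N = 120 is reproduced. Baseline is inside that model as a repeated measure, and the calculation takes no credit for any other covariate. (Section 9.2 calls the effect a main effect; that is a separate matter and is not relied on here.)

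**2. Chance covariates.** P(at least one) = 1 − 0.95^k; expected number = 0.05k.

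| Variables tested, k (assumed) | P(at least one) | Expected number |
|---|---|---|
| 5 | 23% | 0.25 |
| 10 | 40% | 0.50 |
| 15 | 54% | 0.75 |
| 20 | 64% | 1.00 |

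Independence is a simplification, since several pain measures will be correlated. The expected number does not depend on it.

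**3. A comparison with no baseline term.** Take a single follow-up comparison of arms. Unadjusted SE = √(2/60) = 0.183 SD. Always adjusting for a baseline with r = 0.43 multiplies the variance by 1 − 0.43² = 0.815, so SE = 0.183 × √0.815 = 0.165. That is as if 120 patients were 120/0.815 ≈ 147. The normal formula gives power of 27.7% against 32.9% at d = 0.25, and 78.2% against 85.8% at d = 0.5. A simulation of 100,000 trials adds the pre-test rule:

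| | Never adjust | Test, then adjust | Always adjust |
|---|---|---|---|
| Type I error | 5.0% | 4.6% | 5.1% |
| Power, d = 0.25 | 27.5% | 27.3% | 32.3% |
| Power, d = 0.5 | 77.6% | 78.3% | 85.1% |

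The rule behaves much like never adjusting. The loss is 32.3 − 27.3 = 5.0 points and 85.1 − 78.3 = 6.8 points.

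**4. Where the baseline outcome is already in the model.** Keep it in at r = 0.43 and leave one further covariate to the rule. Simulated power, rule against always adjusting:

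| Partial correlation (assumed) | d = 0.25 | d = 0.5 |
|---|---|---|
| 0.1 | 0.327 v 0.327 | 0.848 v 0.850 |
| 0.2 | 0.331 v 0.338 | 0.845 v 0.858 |
| 0.3 | 0.324 v 0.346 | 0.854 v 0.876 |

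The loss is about 0 to 2 points. As a rough ceiling, compare never with always including the further covariate at partial correlation 0.3 and d = 0.5. Its variance factor is 1 − 0.3² = 0.91, so SE falls from 0.165 to 0.165 × √0.91 = 0.157. By the normal formula power rises from 0.858 to 0.889, about 3 points.

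**5. Cost of a useless covariate.** A pure-noise covariate that passes the pre-test raises the SE by about 2.4% on average in simulation and does not bias the effect.

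**The case against.** The strongest reply is that the plan already secures the adjustment that matters most. The outcome's own baseline is usually the best predictor. Section 9.1 controls for it without condition in the 6-month models, the growth curves carry initial level as the intercept, and section 9.2 has baseline as a repeated measure. The rule itself is largely mechanical: tests, alpha and consequence are stated. This is also a feasibility pilot with a descriptive primary aim.

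Most of this stands, and it rules out several stronger readings that a reader might infer:

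- **That every between-arm model loses 5 to 7 power points.** The documents do not support this. The figure comes from omitting the variable with r = 0.43, which is the outcome's own baseline, and the 6-month models already include it.
- **That the rule inflates false positives.** It does not. Simulated type I error is 4.6% at r = 0.43 and 3.6% at r = 0.7.
- **That it weakens the primary aim.** Aim 1 reports percentages and has no covariate model.
- **That a particular number of spurious covariates is to be expected.** The documents give no count of tested variables, so only a range can be shown.

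The reply does not defend the rule itself. Nothing is gained by choosing covariates on arm imbalance, no other prognostic covariate is fixed, and any clinical-outcome comparison outside the stated models, such as one at end of treatment, has no stated baseline term.

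**Conclusion.** The concern holds in a limited form. The rule chooses covariates by chance, each at about 5%, with a 23% to 64% probability of at least one chance covariate for 5 to 20 independent variables. Its cost falls on prognostic covariates other than the baseline outcome, at about 0 to 2 power points for one such covariate with partial correlation 0.1 to 0.3, and on any between-arm comparison left without a baseline term, at about 5 to 7 points at r = 0.43. The number and independence of the tested variables, the partial correlations and the use of 0.43 as the baseline-to-follow-up correlation are assumptions. The effect is modest and confined to the secondary-aim analyses. It is worth correcting because the rule has no offsetting benefit and the better alternative uses variables already collected.

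**What to change.** In section 9.1:

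1. Delete the sentence that begins "Subsequent analyses will adjust for significant baseline differences among the randomized groups", and report baseline characteristics by arm without p-values.
2. Keep the unconditional baseline-outcome adjustment in the 6-month mediation models. Apply it to any other between-arm comparison of a clinical outcome in which baseline is not already a repeated measure.
3. Name a short fixed list from the section 9.6 variables, for example age, gender and pain duration, and include it in the Aim 2 models whatever the observed balance.
4. Do not add the baseline mechanism as a covariate in growth models where it is already the intercept. It would duplicate a quantity that the plan also treats as a candidate mediator.
5. State how the rule on variables associated with missing data combines with the fixed list. Otherwise the models remain data-dependent by that second route.

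The cost is a paragraph of SAP text and a few degrees of freedom. The listed variables are already collected at baseline (section 6.2.2).
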